1.0 Objectives

The goal of this study will be to measure:

- 1) Total narcotic consumption
- 2) VAS pain scores
- 3) Length of stay in the post anesthesia care unit (PACU)

following total hip arthroscopy in two groups of patients, one that receives intra-articular (IA) morphine and clonidine in addition to the standard pre and postoperative analgesia and the other group that receives normal saline in addition to the standard pre and postoperative analgesics.

The primary goal of this study will be to determine if perioperative intra-articular morphine and clonidine injections will reduce the postoperative narcotic consumption, pain scores, and time to recovery for patients undergoing hip arthroscopy.

The primary outcome of this study will be narcotic consumption during PACU recovery duration, which will be measured by total opioid consumption in units of morphine equivalents. PACU opioid consumption will be calculated from the medications list, which is regularly recorded in the electronic medical record.

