8.0 Study Endpoints

The primary endpoint is patient narcotic consumption in the PACU after hip arthroscopy. Narcotic consumption will be measured by converting the patient's opioid consumption during their PACU recovery duration into morphine equivalents. This conversion is necessary to standardize different types of narcotics that can be administered in the PACU. We will also be determining the utility of IA morphine and clonidine in decreasing the patient reported pain in the PACU and during the first postoperative week, time until discharge from the PACU, and the quality of patient recovery using the QoR-15 survey.

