9.0 Procedures Involved

100 patients will be consented for this study. 50 for the "control group" injection and 50 for the "therapeutic group" injection. For patients who are consented and enrolled in this study, prior to surgery, [name] will place a written order to the OR pharmacy for the randomized injection. Each order placed will be associated with a sequential study number (1-100) to keep track of each patient and the intervention that they received. The OR pharmacy will randomize the injection into the control or therapeutic group, so as to keep the team involved in patient care blinded to the intervention.

In the preoperative holding area prior to surgery, all patients will be asked to fill out the QoR-15 questionnaire (see Appendix), rate their current level of pain on the Visual Analog Scale (0-10), and be asked if they have taken any pain medication in the past 24 hours. Those in the control group will receive a 11 mL injection of .9% normal saline, and the therapeutic group will receive a 11 mL injection of 10 mg morphine and 100 mcg of clonidine in .9% NaCl solution. Both injections will occur at the conclusion of the hip arthroscopy procedure. All other pre, peri, and postoperative procedures will follow the standard of care.

Postoperatively, pain scores, amount of narcotics used, and discharge times, which are recorded in the patient's medical record as part of standard of care, will be collected. The control group will be compared to the therapeutic group. All postoperative pain management will follow the normal standard of care procedures for hip arthroscopy patients.

Additionally, patients will be sent home with a short "diary" for logging their pain and narcotic consumption in the first week following surgery. They will be rating their pain and logging narcotic consumption at 6, 18, 24, 48 hours, and 7 days postoperatively. This diary will be collected from the patient at their two week follow-up appointment.

The research procedures required for this protocol include the intra-articular injection at the conclusion of the hip arthroscopy procedure. At

Prospective Assessment of Perioperative Intra-Articular Morphine Injection in Hip Arthroscopy on Postoperative Pain Management

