11.0 Data and Specimen Management

All analyses will use the database with a coded study number as the patient indicator. The data will be analyzed with a Student's T-Test, non-parametric Mann Whitney test, and chi-square test.

All analyses will use the database with a coded study number as the patient indicator. Additionally, all information will be stored in a locked room on a password protected computer. As aforementioned, patient identifiers will be kept separately from medical data. Only the PI will have access to the patient identifier list, and only the PI and co-investigators will have access to the coded database. All non-electronic information, including consent forms, QoR-15 surveys, and patient postoperative diaries will be kept in a locked file cabinet in [name] office.

- The data extracted from the chart review will be maintained in a computer that is located in a secure area accessible only by research personnel of the project via an encrypted password. The computer is password protected and logs out the current user if no activity is detected for five minutes. The electronic data storing patient identifying information will be stored on a single password protected computer in [name] office in the Department of Orthopedics ([name]).
- Data will be stored until the completion of the study, whereupon all data with personally identifying health information will be destroyed. All paper based data will be placed in a locked bin to be destroyed by Citadel Management once the study is complete.

Prospective Assessment of Perioperative Intra-Articular Morphine Injection in Hip Arthroscopy on Postoperative Pain Management

- Only the PI will have access to the patient identifier list, and only the PI and co-investigators will have access to the database for analysis.
- The PI and co-investigators will be the only ones handling data.
- The patient identifier list will never leave the password protected computer in [name] locked office. Any electronic transmission of the coded data will occur over Northwestern's secure Microsoft Outlook email service and will only be accessed through Northwestern's secure remote database, FSMFiles.

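### Repeated diary pain scores have no analysis that uses the baseline score or the five times together; one prespecified mixed-model contrast would serve better

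*Combined protocol and SAP*

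**What the plan says.** Section 9.0 (Procedures Involved) has each patient give a VAS pain score before surgery, then keep a diary at home: "They will be rating their pain and logging narcotic consumption at 6, 18, 24, 48 hours, and 7 days postoperatively". The diary is handed in at the two-week visit.

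Section 8.0 (Study Endpoints) makes pain over that period one of the additional aims: "decreasing the patient reported pain in the PACU and during the first postoperative week". These aims are neither ranked nor labelled secondary.

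The whole statistical method is one sentence in Section 11.0, which lists a Student's t-test, "non-parametric Mann Whitney test, and chi-square test". It does not tie a test to an endpoint or a time. It gives no significance level, multiplicity rule, baseline adjustment or repeated-measures method.

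Section 3.0 leaves a patient out of a particular analysis when essential data are missing, and also allows interpolation without saying how.

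Section 1.0 states the primary goal as whether the injection "will reduce the postoperative narcotic consumption, pain scores, and time to recovery for patients undergoing hip arthroscopy". The same section then names one primary outcome: "The primary outcome of this study will be narcotic consumption during PACU recovery duration". Section 8.0 agrees: "The primary endpoint is patient narcotic consumption in the PACU after hip arthroscopy".

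**The concern.** Each patient can supply five diary pain scores and a baseline score, but the plan does not say how they become an answer about first-week pain. The listed tests compare two groups on one value per patient. Nothing in Section 11.0 says which value that is: one time point, a change from baseline, or a summary over times.

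Two things are at stake. If each time were tested and any significant one reported, chance findings would be more frequent than the nominal rate suggests. If a single time were analysed, the result would be less precise than one drawing on all the scores, and a patient with a gap at that time would be dropped or filled in by an undefined rule.

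The goal sentence in Section 1.0 adds a smaller problem. It is broader than the primary outcome that follows it, and the two should agree.

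**Working it through.** **Inputs from the plan.** 50 patients per arm (Sections 7.0, 9.0 and 23.0); five diary times (Section 9.0); one designated primary outcome (Sections 1.0 and 8.0). The plan gives no figure for false-positive risk or power, so there is none to reproduce.

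**Assumptions.** Two-sided 5% per test; equal correlation ρ between any two diary times; equal SD at each time; complete data; an illustrative effect of 0.4 SD. None of these is stated in the plan.

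**1. False positives if five pain times were tested separately.** Under independence the chance of at least one is 1 − 0.95^5 = 0.226. For correlated scores, simulated two-sample t-tests (50 per arm, 20,000 runs) give:

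| ρ | Chance of at least one p < 0.05 |
|---|---|
| 0 | 22.6% |
| 0.3 | 21.2% |
| 0.5 | 18.4% |
| 0.7 | 14.9% |
| 0.9 | 10.3% |

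Repeated pain scores in one patient are correlated, so the independent figure is an upper value. The primary outcome, tested once, stays at 5%.

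**2. Power from averaging four times (6, 18, 24 and 48 hours).** In units of the single-time variance, the mean of four scores has variance (1 + 3ρ)/4. The standardised effect becomes 0.4/√[(1 + 3ρ)/4]. Power is for a two-sample t-test with 50 per arm.

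| Analysis | Variance factor | Standardised effect | Power |
|---|---|---|---|
| One time | 1 | 0.40 | 51% |
| Mean, ρ = 0.3 | 0.475 | 0.58 | 82% |
| Mean, ρ = 0.5 | 0.625 | 0.51 | 71% |
| Mean, ρ = 0.7 | 0.775 | 0.45 | 61% |
| Mean, ρ = 0.9 | 0.925 | 0.42 | 54% |

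The gain comes from averaging and would be the same for a t-test on each patient's mean. It takes no credit for baseline adjustment.

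**3. Power if the effect is not constant.** If the 0.4 SD effect exists only at 6 hours, the four-time mean carries 0.4/4 = 0.1 SD. At ρ = 0.5 the standardised effect is 0.1/√0.625 = 0.13 and power is about 10% (11% at ρ = 0.3, 9% at ρ = 0.7). A test at 6 hours alone has 51%. If the effect exists at 6 and 18 hours only, the mean carries 0.2 SD and power is about 24% (30% to 20% for ρ = 0.3 to 0.7).

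**The case against.** A reader might infer that the diary is designed for five separate tests. The documents do not support that. Section 9.0 lists collection times, Section 11.0 lists tests without linking them to times, and Section 8.0 frames first-week pain as a single question. A t-test or Mann-Whitney test on each patient's mean or area under the curve fits the text equally well and, with complete data, would deliver the whole averaging gain above. This objection stands: the false-positive figures are conditional, and the gain is not peculiar to a mixed model.

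A reader might also infer that the three-outcome goal inflates the primary test. It would do so only if success on any one of the three counted as meeting the goal, and no section says that. Sections 1.0 and 8.0 name the same single outcome, so this is a mismatch of wording.

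It is also fair to say that averaging can hurt. The treatment is one injection at the end of surgery, and an effect confined to the first hours would be diluted. A 6 to 48 hour window also leaves out day 7, although Section 8.0 asks about the first week.

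What remains is that the plan chooses no summary, makes no stated use of the baseline score, and leaves gaps to exclusion or an undefined interpolation. A two-sample test on a patient mean would not settle how to treat partly completed diaries. The mixed model uses their available entries, assuming data are missing at random.

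**Conclusion.** The concern holds in a limited form. Diary pain is measured repeatedly with a baseline, and Section 11.0 specifies nothing that uses these together. A prespecified repeated-measures model is a better method at little cost.

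Separate testing, which is possible but not stated, would carry a false-positive chance of about 10% to 21% for correlations of 0.9 to 0.3. For a constant 0.4 SD effect, one contrast averaged over 6 to 48 hours would raise power from 51% to between 61% and 82% for correlations of 0.7 to 0.3. Baseline adjustment and use of partial diaries come on top and are not quantified here. The power gain reverses if the effect is only early.

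All of this concerns non-primary results. The primary comparison of PACU morphine equivalents is unaffected.

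**What to change.** **Section 11.0.** Analyse diary VAS with one linear mixed model for repeated measures, with terms for arm, time, arm by time and pre-operative VAS. Use all available entries and do not interpolate. Name one treatment contrast in advance. The model alone does not limit the number of claims; naming the contrast does. Report the arm difference at every time, including day 7, as an estimate with a 95% confidence interval and no separate claim.

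**Choice of window.** The investigators should fix the window before unblinding. They should weigh the gain under a lasting effect against the loss under an early one, and state how the window answers the first-week aim in Section 8.0.

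**Section 1.0.** Reword the primary goal to match the named primary outcome, and label the other outcomes secondary.

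**Cost.** Wording in two sections and a standard model, with no extra patients or data. One favourable time point could no longer be claimed on its own, and an averaged contrast risks missing a short-lived effect.

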10.0 Data and Specimen Banking

To maintain patient confidentiality, the study coordinator will assign an arbitrarily generated identification number to each patient. This patient identifier list will be kept separately from the study database on an encrypted computer in [name] office. All study data will be entered into an MS Excel Database created by [name]. The data will be entered into the database in [name] office by the research coordinators—no personal information containing identifiers will be used. The consent forms and QoR-15 surveys will be kept in a locked file in [name]

Prospective Assessment of Perioperative Intra-Articular Morphine Injection in Hip Arthroscopy on Postoperative Pain Management

office until the completion of the research project. Only the PI and co-investigators will have access to the coded database. The OR pharmacy will have a numbered list that connects each patient to the intervention that they received via randomization.

In summary, all information that includes personally identifying information, such as name or medical record number, is not entered into the database with the medical information. Identifying information is only entered into a separate database that links the patient to an arbitrary study number. This identifying list will be kept only in [name] office, under his control. A separate list will be kept by the OR pharmacy to track which patients received the control or study group intervention. The plan to destroy the identifiers will be accomplished by a program designed to permanently erase "destroy" all subject identifiers after the completion of the study. The paper based data will be placed in a locked bin which will be permanently destroyed by Citadel Management.

No data will be shared with anyone other than the co-investigators of this study.

11.0 Data and Specimen Management

All analyses will use the database with a coded study number as the patient indicator. The data will be analyzed with a Student's T-Test, non-parametric Mann Whitney test, and chi-square test.

All analyses will use the database with a coded study number as the patient indicator. Additionally, all information will be stored in a locked room on a password protected computer. As aforementioned, patient identifiers will be kept separately from medical data. Only the PI will have access to the patient identifier list, and only the PI and co-investigators will have access to the coded database. All non-electronic information, including consent forms, QoR-15 surveys, and patient postoperative diaries will be kept in a locked file cabinet in [name] office.

- The data extracted from the chart review will be maintained in a computer that is located in a secure area accessible only by research personnel of the project via an encrypted password. The computer is password protected and logs out the current user if no activity is detected for five minutes. The electronic data storing patient identifying information will be stored on a single password protected computer in [name] office in the Department of Orthopedics ([name]).
- Data will be stored until the completion of the study, whereupon all data with personally identifying health information will be destroyed. All paper based data will be placed in a locked bin to be destroyed by Citadel Management once the study is complete.

Prospective Assessment of Perioperative Intra-Articular Morphine Injection in Hip Arthroscopy on Postoperative Pain Management

- Only the PI will have access to the patient identifier list, and only the PI and co-investigators will have access to the database for analysis.
- The PI and co-investigators will be the only ones handling data.
- The patient identifier list will never leave the password protected computer in [name] locked office. Any electronic transmission of the coded data will occur over Northwestern's secure Microsoft Outlook email service and will only be accessed through Northwestern's secure remote database, FSMFiles.

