2.0 Background

Since January 2015 many of [name] patients have been receiving IA morphine and clonidine injections as prophylaxis for postoperative pain control after hip arthroscopy. However, prior to January 2015 IA morphine and clonidine were not administered as standard of care.

Because there is so little published about the efficacy of such injections in hip arthroscopy, the purpose of this study is to further explore this gap in knowledge.

A retrospective pilot study at Northwestern Memorial Hospital (under IRB STU00200639) has shown the proposed intervention to be successful in decreasing postoperative narcotic consumption. The control group receiving only the current standard of care had a 40 mEq narcotic consumption, while the interventional group receiving the additional IA morphine and clonidine had only a 23 mEq narcotic consumption ($p=.0259$).

Over the last few decades, the use and safety of arthroscopic hip surgery has considerably improved though the evolution and development of arthroscopic imaging and instrumentation¹. There is still a considerable amount of room for growth and research in comparison to arthroscopic knee and shoulder surgery, which have been around much longer. One area which needs attention is postoperative pain management for patients undergoing hip arthroscopy. The benefits to controlling postoperative pain are multifocal and range from improved patient comfort and decreased

Prospective Assessment of Perioperative Intra-Articular Morphine Injection in Hip Arthroscopy on Postoperative Pain Management

time of recovery to decreased narcotic consumption and reduced cost of care².

Many studies on the use of intra-articular morphine (IA) injections in arthroscopic knee surgery have demonstrated effectiveness in reducing both patient reported pain and narcotic consumption post-operatively³⁻⁵. Furthermore, studies have shown that intra-articular clonidine, an α_2 agonist, potentiates the analgesic effect of morphine when the two are used in combination⁶. While there is considerable evidence supporting the use of IA morphine for knee surgery, very little has been cited for such use in hip arthroscopy⁷. The purpose of our study is to expand upon the retrospective data that we have already analyzed to better assess the effectiveness of IA morphine and clonidine injections in reducing patient reported pain and narcotic consumption.

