3.0 Inclusion and Exclusion Criteria

All patients who are undergoing a hip arthroscopy procedure by the senior surgeon ([name]) will be approached to participate in the study, with the exception of pregnant women, adults unable to consent, prisoners, and any patient under the age of 18 years.

Any patient with a medical contraindication to morphine or clonidine will not be included in either the therapeutic or control group. Additionally, for the final analysis, the data for all subjects in our data set will be analyzed using a random study number as the key identifier. In some cases, if there is substantial data missing for a subject, which would be otherwise essential for analysis, the subject's information for that particular analysis will be excluded. To the best extent possible, data that can be interpolated will be utilized.

4.0 Study-Wide Number of Subjects:

N/A

5.0 Study-Wide Recruitment Methods:

N/A

6.0 Multi-Site Research:

N/A

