the conclusion of the hip arthroscopy, before closing the incision with sutures, an intra-articular injection of both morphine and clonidine, for the therapeutic group, or normal saline, for the control group, will be performed. All other operative procedures will occur as standard of care to ensure optimal patient safety.

- All standard of care procedures will take place for a hip arthroscopy procedure. No additional procedures are needed to reduce the magnitude of risk, as patients with a contraindication to morphine or clonidine will not be enrolled in the study, and patients will be under the watch of nurses, physician assistants, and doctors while in the postoperative recovery room.
- The only drugs used in this study that are beyond the standard of care for hip arthroscopy are intra-articular morphine and clonidine. In the context of this study, morphine and clonidine are FDA approved drugs for non-approved use. The control group will receive intra-articular normal saline, which is FDA approved.
- Northwestern's Powerchart electronic medical record system will be used to access patient medical records for those who consent to the study. Basic patient demographics, pre and post-op VAS pain scores, discharge times, and narcotic/analgesic consumption will be recorded from data in the medical records. The QoR-15 survey will also be used to assess patient quality of recovery. All data will be coded and stored in the attached Excel spreadsheet, which will be on a database in [name] locked office, only accessible to research personnel of the project via an encrypted password. All paper based documents will be kept in a locked cabinet in [name] office.

All data collected for this study can be found in the attached MS Excel spreadsheet and sample QoR-15 survey. Data points include age, sex, height, weight, tobacco use, VAS pain scores, discharge times, duration of surgery, discharge criteria score, medication use, and the following quality of recovery scores (as seen in the QoR-15): comfort, independence, and support. The postoperative diary will be asking patients for VAS pain scores, narcotic consumption, and potential complications at 6, 18, 24, 48 hours, and 7 days postoperative.

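### Section 11.0 ties no test to the primary endpoint, and the baseline pain and analgesic data planned for every patient enter no analysis: a loss of precision, not of validity

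*Combined protocol and SAP*

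**What the plan says.** - **Endpoint (section 8.0).** "The primary endpoint is patient narcotic consumption in the PACU after hip arthroscopy", converted to morphine equivalents. Section 1.0 agrees. Neither section names a test.
- **Analysis (section 11.0).** "The data will be analyzed with a Student's T-Test, non-parametric Mann Whitney test, and chi-square test". No endpoint, rule for choosing between tests, significance level or effect estimate is attached. Section 9.0 adds only this: "The control group will be compared to the therapeutic group".
- **Baseline data (section 9.0).** In preoperative holding each patient completes a 0-10 VAS for pain and will "be asked if they have taken any pain medication in the past 24 hours". The second item, as worded, gives a yes/no answer. The chart is a further source: "pre and post-op VAS pain scores, discharge times, and narcotic/analgesic consumption will be recorded from data in the medical records". No section mentions covariates, regression, change from baseline or stratified randomisation.
- **Size (section 23.0).** 100 patients, 50 per group, with no alpha, power or SD.
- **Pilot (section 2.0).** 40 versus 23 mEq, p = .0259, with no SD, no pilot sample size and no test named.

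**The concern.** Two things are left open. First, chi-square does not suit a continuous endpoint, so either the t-test or Mann-Whitney could decide the primary comparison. If opioid use is skewed, the two can disagree about significance, and the plan does not say which one counts.

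Second, preoperative pain and recent analgesic use may well predict opioid use in the PACU. They are measured before the injection, so adjusting for them is legitimate. With the sample fixed at 100 and no stated power basis, adjustment could narrow the confidence interval at almost no cost. As written, that option is unused.

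**Working it through.** **1. The plan's own figure.** N = 100 cannot be reproduced, because alpha, power and SD are absent. With a 17 mEq difference (40 − 23) and two-sided 0.05, a t-test with 50 per arm has 80% power only if the SD is about 30.3 mEq: 17 / [(1.960 + 0.842) × √(2/50)] = 30.3.

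**2. What adjustment can do in principle.** Residual variance is multiplied by 1 − R². At R² 10% the CI width is multiplied by √0.90 = 0.949, equivalent to 50/0.90 = 55.6 patients per arm. At R² 30% the factor is √0.70 = 0.837, equivalent to 50/0.70 = 71.4 per arm. At R² 0 there is no gain.

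**3. Simulation under skew.**
- From the documents: 50 per arm; 40 and 23 mEq.
- Assumed: 40 and 23 are arm means of PACU use; lognormal outcome with the same CV in both arms; one continuous and one binary covariate (40% yes) with joint R² on the log scale; two-sided 0.05.
- 6,000 trials per power cell. The simulation standard error is about 0.4 points at 90% power (√(0.9 × 0.1/6000)) and 0.6 points at 70%.

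Power (%) at R² 0 / 10 / 20 / 30%:

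| CV | Mann-Whitney, unadjusted | Rank regression, adjusted | Gain at R² 10% | Gain at R² 30% |
|---|---|---|---|---|
| 0.75 | 97.7 / 98.2 / 97.9 / 98.0 | 97.5 / 98.7 / 99.2 / 99.7 | 0.5 | 1.7 |
| 1.0 | 89.9 / 89.0 / 89.4 / 88.8 | 89.4 / 90.9 / 94.1 / 96.4 | 1.9 | 7.6 |
| 1.25 | 78.5 / 78.4 / 77.1 / 78.9 | 77.9 / 81.4 / 84.7 / 89.5 | 3.0 | 10.6 |
| 1.5 | 68.9 / 70.3 / 68.9 / 69.2 | 68.1 / 73.5 / 76.8 / 82.2 | 3.2 | 13.0 |

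At CV 1.0 the 95% CI half-width for the rank difference falls from 11.04 ranks (R² 0) to 9.32 (R² 30%). The ratio is 0.844, close to the 0.837 in step 2. Type I error of the rank regression is 4.6-5.4%.

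**4. Model in mEq.** A linear model with HC3 robust standard errors has power of 77.0 / 81.2 / 83.4 / 86.6% at CV 1.0 and 46.7 / 50.5 / 53.1 / 55.8% at CV 1.5. The unadjusted t-test has about 80% and 50%.

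**5. Which listed test counts.** The t-test and Mann-Whitney fall on different sides of 0.05 in 3-4% of trials (CV 0.75), 13-14% (CV 1.0), 22-23% (CV 1.25) and 26-28% (CV 1.5). About 83-86% of these disagreements have Mann-Whitney significant and the t-test not.

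**6. Type I error.** Choosing one test by a normality check gives 4.8-5.4%. Counting either test as a success gives about 6% for normal data and 7-8% for skewed data.

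**7. Missing covariates.** With both covariates missing in 5, 10 or 20 of 100 patients and filled with overall means blind to group, power at CV 1.0 and R² 30% is 96.2, 95.8 and 94.8%, against 96.4% with full data and 88.8% for Mann-Whitney. Type I error stays at 4.5-5.5%.

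**The case against.** Collecting a baseline item does not oblige a trial to adjust for it, and the unadjusted comparison is valid under randomisation. A t-test, a Mann-Whitney and a chi-square listed together read naturally as a conventional choice by data type and distribution, which keeps type I error near 5%. The test disagreements mostly reflect the t-test's lower power under an assumed skew. The larger gains need R² 30% from one pain score and one yes/no item, and nothing in the documents supports that value. One sentence naming a test would close the gap, whereas adjustment brings its own missing-covariate problem.

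Much of this stands, and it rules out several stronger readings:
- A reader might infer that the planned comparison is biased. It is not.
- A reader might infer that the sponsor means to report whichever test is significant, with error of 6-8%. The documents do not plan that, although section 11.0 does not state the conventional rule either.
- A reader might take 40 and 23 mEq as PACU means. Section 2.0 describes postoperative consumption and does not call the figures means.
- A reader might think section 3.0 already permits covariate imputation through "To the best extent possible, data that can be interpolated will be utilized". That sentence does not specify mean imputation of a covariate, and the sentence before it excludes patients with substantial essential data missing from the analysis concerned.

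The objection does not remove the point itself: no primary analysis is named, and baseline data planned for every patient go unused when using them costs almost nothing.

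**Conclusion.** The point holds as a matter of precision and completeness, and the change should be made. The text is clear that section 11.0 lists only unadjusted tests, ties none to the primary endpoint, and leaves the two baseline items without an analytic role.

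The size of the loss cannot be known from the documents. Under the assumptions shown, adjustment gains nothing if the covariates predict nothing, about 1 to 4 points of power at R² 10%, and about 8 points (CV 1.0) to 13 points (CV 1.5) at R² 30%. At CV 0.75 power is already about 98% and there is little to gain. The unnamed test on its own is mainly missing detail, but under marked skew it could decide whether the trial is called positive. Only the sample size and the 40 and 23 mEq figures come from the documents; their use as arm means, the outcome distribution, CV, R² and covariate prevalence are assumed.

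**What to change.** In section 11.0, before unblinding:

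1. Name one primary analysis of PACU morphine equivalents at two-sided 0.05, adjusted for preoperative VAS and 24-hour analgesic use (yes/no), with the effect estimate and 95% CI from that same model. Choose one of:
   - **Rank regression.** Rank the outcome over all patients and regress the rank on group and the two covariates. This has better power under skew, but the effect is in ranks or a probability. The rank difference divided by the number of patients, plus 0.5, is the probability that a control patient uses more than a therapeutic patient. At CV 1.0 that is 18/100 + 0.5 = 0.68.
   - **Linear model with robust standard errors.** The effect stays in mEq, with lower power under skew. State the variance estimator: at CV 1.0 and R² 0, HC3 costs about 3 points of power against the t-test and HC1 about 1.
2. Label the unadjusted t-test and Mann-Whitney as sensitivity analyses.
3. Add a new rule that a missing baseline covariate is filled with the overall mean (or overall proportion for yes/no), blind to group, so that adjustment drops no patient.
4. Adjust postoperative pain scores for preoperative VAS.

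The cost is analysis wording and two degrees of freedom, with no gain if the covariates predict nothing (89.4% versus 89.9% power at CV 1.0). The missing time for a postoperative QoR-15 is a separate issue and is not part of this change.
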